#### 4.4.5 SIAQ

tion < mil

#### 4.4.6 Self-administration at home

Zation The ability of study participants with gMG to successfully self-administer rozanolixizumab at home after training in the self-administration technique using the syringe driver and manual push methods will be assessed after each administration at home (Visits 10, 11, 12 for Self-administration Period 1 and Visits 16, 17, 18 ] for Self-administration Period 2). Successful self-administration includes a correct SC infusion with the intended dose at the correct infusion site by the participant and will be assessed by the site via a mandatory direct contact with the study participant via telephone or video call as soon as possible after each home self-administration.

The number and proportion of participants deemed a treatment success at each of the 3 home self-administration visits will be tabulated by period and overall for each self-administration method for the RSS.

The missing data will not be imputed.

The self-administration data will be listed for the SS.

#### 4.4.7 TEAEs leading to permanent withdrawa

The safety and tolerability of rozanolixizumab in study participants with gMG will be assessed considering the occurrence of TEAEs leading to permanent withdrawal of rozanolixizumab during the study in the SS.

The occurrence of TEAEs leading to permanent withdrawal of rozanolixizumab will be summarized during the Self-administration Periods by the number and proportion of participants separately by period and overall for each self-administration method. This will be included in the AEs overview table. TEAEs leading to permanent withdrawal of rozanolixizumab will also be summarized for SS and RSS by System Organ Class (SOC), High Level Term (HLT) and Preferred Term (PT).

Occurrence of TEAEs leading to permanent withdrawal of rozanolixizumab during the Training Period will also be summarized overall.

#### Other safety analysis 4.5

#### Extent of exposure 4.5.1

Study medication duration (days) will be summarized overall for the SS for Training Period and overall. For the RSS, study medication duration will be summarized also by Treatment Periods and overall. It will be calculated as:

Date of last study medication infusion - Date of first study medication dosing + 1

The study medication duration will also be described by category:  $\geq 1$  day,  $\geq 36$  days,  $\geq 78$  days, and  $\geq$  120 days.

The number of administrations done by an HCP will be summarized overall from the date of first infusion to the last infusion.

Study medication duration (days) will also be reported overall for each period separately 12tion (Training period/Self-administration Period 1/ Self-administration Period 2). It will be calculated as:

Date of last study medication infusion within the period - Date of first study medication • dosing within the period +1

The duration of infusion (in minutes) using self-administration treatment will be summarized for ting autred the RSS by method and timepoint. It will be derived as:

Duration of infusion (minutes) = Infusion stop time – Infusion start time.

All study medication administration details will be listed.

#### 4.5.2 **Adverse events**

All AEs and SAEs will be collected from the signing of the informed consent form until the End of Study Visit (Visit 21) and will be coded (Section 6.2). TEAE definition is available in Section 4.3.1.1.

The following summaries will be provided overall for the SS and by period and overall for each self-administration method and overall for the RSS. Adverse events will be presented by SOC, HLT and PT:

- Incidence of AEs overview including any TEAEs, serious TEAEs, participant study discontinuations due to TEAEs, drug-related TEAEs, severe TEAEs, AEs leading to death, TEAEs leading to death. AEs leading to death will be reported for all screened participants in the table produced for SS.
- Incidence of TEAEs •
- Incidence of TEAEs by Maximum Intensity
- Incidence of TEAEs by Intensity
- Incidence of TEAEs by Maximum Relationship
- Incidence of TEAEs by Relationship
- Incidence of Treatment-Emergent Serious AEs
- Incidence of TEAEs Leading to Study Discontinuation
- Incidence of non-serious TEAEs above reporting threshold of 5% of study participants
- Incidence of drug-related TEAEs
- Incidence of severe TEAEs
- Incidence of TEAEs leading to death
- Incidence of treatment emergent adverse event of special interest (AESI)
- Incidence of treatment emergent adverse event of special monitoring (AESM) by type of AESM

Drug-related is based on the Investigator assessment.

AESIs are the cases of potential Hy's Law (cf. Section 4.5.3.1.2).

AESMs include severe and/or serious headache, suspected aseptic meningitis and medication error associated with adverse reaction(s).

ation AESMs and AESIs will be identified based on the assessment by the Investigator as recorded in the CRF. An AE will be counted as an AESM if there is a 'yes' response to the question "Adverse event of Special Monitoring?" and 'no' otherwise. An AE will be counted as an AES if there is a 'yes' response to the question "Adverse Event of Special Interest?" and 'no' otherwise.

When applicable adverse event summaries will be ordered by alphabetical SOC, HLT and decreasing frequency of PT within SOC and HLT in the RLZ total column for tables.

Listings of all AEs, all non-serious TEAEs, serious TEAEs, permanent withdrawal of IMP due to TEAEs, study participant discontinuation from study due to AEs, AEs leading to death, AESIs, and AESMs will be presented by sequence (if applicable), period (if applicable) and participant for the SS. AE duration will be included in the listings. Hospitalization data will be listed.

Rozanolixizumab treatment-emergent adverse events of focus (TEAEOF) will also be analysed for the SS. TEAEOF are defined in Section 6.13. The number and percentage of study participants who experience each category of the TEAEOF will be summarized. The following summaries will be presented by SOC, HLT and PT:

- TEAEOF (presented also for RSS)
- Serious TEAEOF
- TEAEOF by maximum intensity (mild, moderate and severe)

A by-subject listing of all TEAEOF by category (as listed above) will be provided. Further details related to the statistical analysis of the above mentioned treatment-emergent AEOFs are provided in Section 6.13.

#### 4.5.3 Additional safety assessments

#### 4.5.3.1 **Clinical laboratory evaluations**

The following table (Table 4-4) lists safety laboratory assessments that are collected throughout the study. Laboratory assessments are performed predose.

	Laboratory Assessments		Parameters
	Hematology	Platelet count	White blood cell (WBC) Count with Differential:
.0	0	Red blood cell (RBC)	Neutrophils
i'S		count	Lymphocytes
•		Hemoglobin	Monocytes
		Hematocrit	Eosinophils Basophils

## Table 4–4: Protocol-required safety laboratory assessments

Rozanolixizumab

Laboratory Assessments	Parameters			
Clinical Chemistry a	Blood Urea Nitrogen (BUN)	Potassium	Aspartate Aminotransferase (AST)/ Serum Glutamic- Oxaloacetic Transaminase (SGOT)	Total and direct bilirubin
	Creatinine	Sodium	Alanine Aminotransferase (ALT)/ Serum Glutamic- Pyruvic Transaminase (SGPT)	Total Protein Albumin
	Glucose (fasting state preferred) b	Calcium	Alkaline phosphatase	C-reactive protein (CRP)
	Lactate dehydrogenase (LDH)	Triglycerides	Low-density lipoprotein (LDL) High-density lipoprotein (HDL)	Total Cholesterol
Routine Urinalysis	
 
Specific gravity
 
pH, glucose, protein, blood, ketones, albumin, bilirubin, urobilinogen, nitrite, leukocyte esterase by dipstick
 
Microscopic examination (if blood or protein is abnormal)
 
			
Other Screening Tests	• Follicle-stimulating hormone and estradiol (as needed in women of non-childbearing potential only)			
	
 
Serum or urine human chorionic gonadotropin (hCG) pregnancy test (as needed for women of childbearing potential)c
 
			
	• Serology testing (for human immunodeficiency virus, Hepatitis B, and Hepatitis C)			
	All study-required laboratory assessments will be performed by a central laboratory.			
	The results of each test must be entered into the CRF.			
NOTES :	XV	0		
	sessments that may meningitis, see pr		ase of AESM of severe and/or ser	ious headache or

suspected aseptic meningitis, see protocol Table 1-3.

a Details of liver chemistry stopping criteria and required actions and follow-up assessments after liver stopping or monitoring event are given in the protocol Section 7.1.1 and Appendix 6 (Section 10.6). All events of ALT  $\geq$ 3 × upper limit of normal (ULN) and bilirubin  $\geq$ 2 × ULN (>35% direct bilirubin) or ALT  $\geq$ 3 × ULN and international normalized ratio (INR) >1.5, if INR measured, may indicate severe liver injury (possible Hy's Law) and must be reported as an SAE (excluding studies of hepatic impairment or cirrhosis).

b To be done at Screening only

Local urine testing will be standard for the protocol unless serum testing is required by local regulation or IRB/IEC.

## 4.5.3.1.1 Laboratory values over time

Hematology, clinical chemistry and quantitative urinalysis (observed value, absolute change from Baseline) will be summarized in standard units using descriptive statistics for the Training

period overall for the SS, for the Self-administration period by period and overall for each selfadministration method for the RSS and for the Follow-up period overall for the RSS.

Central laboratory data will be used for the summary tables and figures. Local laboratory data will be listed only.

stion Measurements below the lower limit of quantification (BLQ) will be imputed with half of the lower limit of quantification (LLOQ), and measurements above the upper limit of quantification (ALQ) will be imputed to the upper quantification limit for the purpose of quantitative summaries. Handling of repeated measurements is described in Section 6.8.1.

An assessment is markedly abnormal (MA) if it meets the MA criteria outlined in Section 6.9

Treatment-emergent (TE) is defined as meeting the criteria at any post-Baseline visit after the first infusion of study medication and within 56-days of the last infusion and not meeting the same criteria at Baseline (see SAP section 4.1.2).

A TE assessment will be assigned to the Training period if the start date of the assessment is on or after the date of the first administration of rozanolixizumab during the Training Period and before the first administration of rozanolixizumab in Self-administration Period 1.

A TE assessment will be assigned to the Self-administration Period 1 if the start date of the assessment is on or after the date of the first administration of rozanolixizumab in Selfadministration Period 1 and before the first administration of rozanolixizumab in Selfadministration Period 2.

A TE assessment will be assigned to the Self-administration Period 2 if the start date of the assessment is on or after the date of the first administration of rozanolixizumab in Selfadministration Period 2 and up to the end of Visit 20 assessments (EOT date).

The number and percentage of participants who have TEMA clinical chemistry and hematology assessments at any visit (including unscheduled visit) will be summarized for the Training Period using the SS and by Treatment Period and follow-up for each self-administration method for the RSS.

The laboratory variables that are categorized as normal, high or low based on the reference range supplied by the analytical laboratory will be presented in shift tables from Baseline to any post-Baseline visit (including unscheduled visit) overall for the SS. Values of raw calcium will be used in shift tables, whereas corrected calcium is used for markedly abnormal assessments as outlined in Section 6.9.

Mean values in serum albumin, C-reactive protein, White Blood Cell Count with absolute count and differential (neutrophils, lymphocytes, monocytes, eosinophils and basophils) and platelets will be plotted overall for the SS.

Unscheduled visits assessment will not be included in the summary statistics. All laboratory test results will be listed, including Baseline, scheduled and unscheduled visits with results in standard unit. Values outside the reference range for the continuous variables will be flagged in the listings. The reference ranges will also be reported in the listings. Additional laboratory test, including pregnancy testing, will also be listed.

Stion

#### 4.5.3.1.2 Potential drug-induced liver injury

The number and percentage of study participants who meet one or more of the following potential drug-induced liver injury (pDILI) criteria will be summarized overall for the SS:

- Participants with at least one post-Baseline liver laboratory assessment •
- Incidence of Potential hepatotoxicity with symptoms potentially associated with hepatitis or hypersensitivity according to the Investigator.
- Incidence of Potential hepatotoxicity with no symptoms potentially associated with hepatitis eting autrai or hypersensitivity according to the Investigator.
- Laboratory criteria for pDILI:
  - (AST or ALT  $\ge$  3 x ULN) and TBL  $\ge$  1.5 x ULN
  - (AST or ALT  $\geq$  3 x ULN) and TBL  $\geq$  2 x ULN
  - (AST or ALT  $\ge$  3 x ULN) and TBL  $\ge$  2 x ULN and ALP < 2 x ULN (potential Hy's Law)

In order to meet the above criteria, a study participant must experience the elevation in bilirubin and ALT or AST (and the absence of the ALP elevation) at the same visit. For example, a study participant who experiences a  $\geq 2xULN$  elevation of bilirubin at one visit and a  $\geq 3xULN$ elevation in ALT (or AST) at a subsequent visit has not fulfilled the Hy's law criteria. If participant meets part of one criterion but at least one parameter is unknown, then he/she should not be considered for meeting the criterion.

Additional analyses for liver function tests (LFTs) will be performed to assess the potential for liver toxicities in accordance with the United States Food and Drug Administration guidelines. Per guidelines, the following criteria will be used to define levels of LFT elevation:

- Aspartate aminotransferase (AST):>3 x ULN, >5 x ULN, >8 x ULN, >10 x ULN, >20 x • ULN
- Alanine aminotransferase (ALT): >3 x ULN, >5 x ULN, >8 x ULN, >10 x ULN, >20 x ULN
- AST or ALT: >3 x ULN, >5 x ULN, >8 x ULN, >10 x ULN, >20 x ULN
- Total bilirubin (TBL): >1.5 x ULN, >2 x ULN
- Alkaline phosphatase (ALP) >1.5 x ULN

The number and percentage of study participants who meet one or more of the above LFT elevation criteria will be summarized overall for the SS.

A listing will also be provided for study participants who meet at least one of the above criteria. All results obtained at that visit for the specified parameters will be displayed.

Lifestyle, family medical history, symptoms of hepatitis and hypersensitivity, potential hepatotoxic medications inquiry and hepatic event supplemental medical history data, PK blood sampling will be listed for pDILI.

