- 13. Study participant has 12-lead electrocardiogram (ECG) at Screening (Visit 1) with findings considered to be clinically significant upon medical review. The clinical significance of the findings needs to be assessed by the investigator to determine eligibility.
- 14. Study participant has >3.0xULN of any of the following: alanine aminotransferase (ALT), aspartate aminotransferase (AST), or alkaline phosphatase (ALP) at Screening (Visit 1).
 - If participant has >upper limit of normal (ULN) for ALT, AST, or ALP that does not meet the exclusion limit at Screening (Visit 1), repeat the tests, if possible, before dosing to ensure there is no further ongoing clinically relevant increase.

- For participants with a Baseline result >ULN for ALT, AST, ALP, or total bilirubin, a
 Baseline diagnosis and/or the cause of any clinically meaningful elevation must be
 recorded in the CRF.
- 15. Study participant has bilirubin >1.5xULN at Screening (Visit 1) (unless confirmed Gilbert's syndrome). If participant has elevations only in total bilirubin, the fractionate bilirubin needs to be checked, to identify possible undiagnosed Gilbert's syndrome (ie, direct bilirubin <35%).
- 16. Current unstable liver or biliary disease, at Screening (Visit 1), per investigator assessment defined by the presence of ascites, encephalopathy, coagulopathy, hypoalbuminemia, esophageal or gastric varices, persistent jaundice, or cirrhosis. NOTE: with exception of stable hepatobiliary conditions (including Gilbert's syndrome, asymptomatic gallstones).
- 17. Presence of Hepatitis B surface antigen (HBsAg) or positive Hepatitis C antibody test result at Screening (Visit 1). Note: a study participant with a positive hepatitis C antibody test due to prior resolved disease can be enrolled only if a confirmatory negative Hepatitis C RNA test is obtained.
- 18. Study participant tests positive for human immunodeficiency virus at Screening (Visit 1).
- 19a. Study participant has active malignant neoplastic disease or history of malignant neoplastic disease within 5 years of study entry before Screening (Visit 1) (except for basal or squamous cell carcinoma of the skin or carcinoma in situ of the uterine cervix that have been definitively treated with standard of care approaches or thymoma that did not require chemotherapy and/or radiotherapy after removal).

Other

20. Study participant has a lifetime history of

as indicated by a positive

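### The liver-test elevation count in SAP 4.5.3.1.2 has no post-Baseline window and ignores Baseline status, so ALP and bilirubin elevations present at entry are counted with new ones

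*SAP*

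**What the plan says.** SAP 4.5.3.1.2 plans two liver summaries, both overall for the Safety Set.

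- **pDILI summary.** It opens with the row "Participants with at least one post-Baseline liver laboratory assessment". Rows for potential hepatotoxicity with and without symptoms follow. Three laboratory combinations come last, each needing AST or ALT of at least 3 x ULN and raised bilirubin at the same visit.
- **LFT elevation summary.** ALT and AST are graded from above 3 x ULN upward. The other two parameters are "Total bilirubin (TBL): >1.5 x ULN, >2 x ULN" and "Alkaline phosphatase (ALP) >1.5 x ULN". The reporting sentence reads "The number and percentage of study participants who meet one or more of the above LFT" elevation criteria. It names no visits and makes no comparison with Baseline. A listing then shows, for anyone who meets a criterion, the results from the visit concerned.

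Eligibility is set in Protocol 5.2. Exclusion 14 reads "Study participant has >3.0xULN of any of the following: alanine aminotransferase (ALT), aspartate aminotransferase (AST), or alkaline phosphatase (ALP) at Screening (Visit 1"). Exclusion 15 reads "Study participant has bilirubin >1.5xULN at Screening (Visit 1) (unless confirmed" Gilbert's syndrome) and states no upper limit for that exception.

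SAP 4.5.3.1.1 defines treatment-emergent laboratory abnormality. The value must follow the "first infusion of study medication and within 56-days of the last infusion and not meeting the" same criterion at Baseline. That rule serves the marked-abnormality tables and is restated for vital signs and ECG. Section 4.5.3.1.2 does not invoke it.

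**The concern.** The LFT summary is meant to help judge whether the drug may harm the liver. To do that for ALP and bilirubin, it has to separate values that rose on treatment from values that were already high. As written it cannot, because two of its cut-offs lie inside the range that eligibility admits. No untreated arm shows how many such values would be expected without the drug. In a small study, one or two carried-in elevations would visibly change the reported percentage.

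**Working it through.** The plan states no figure for this count, so there is none to reproduce. The check compares entry limits with cut-offs, applies the possible counting rules to example profiles, and then sizes the effect under stated assumptions.

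**1. Entry limit against lowest LFT cut-off**

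| Test | Admitted at Screening (Protocol 5.2) | Lowest cut-off (SAP 4.5.3.1.2) | Admitted but already above it |
|---|---|---|---|
| ALP | up to 3.0 x ULN | >1.5 x ULN | above 1.5 and up to 3.0 x ULN, any participant |
| Total bilirubin | up to 1.5 x ULN; no limit stated for confirmed Gilbert's | >1.5 x ULN | confirmed Gilbert's only |
| ALT, AST | up to 3.0 x ULN | >3 x ULN | none at Screening |

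**2. Counting rules on example ALP profiles** (x ULN at Screening, Baseline and two later visits; cut-off >1.5)

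| Profile | As written | Post-Baseline samples only | Treatment-emergent rule |
|---|---|---|---|
| 2.0, 2.0, 2.0, 2.0 | counted | counted | not counted |
| 2.0, 2.0, 1.2, 1.0 | counted | not counted | not counted |
| 1.0, 1.0, 1.8, 1.0 | counted | counted | counted |
| 1.0, 1.0, 1.0, 1.0 | not counted | not counted | not counted |

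The first row is the main one. A stable carried-in elevation is counted even on the natural assumption that only post-Baseline samples are used. A window alone removes the second profile but not the first; that needs Baseline status.

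**3. Do other tables separate the two groups?**

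- The shift tables in SAP 4.5.3.1.1 use low, normal and high. A stable ALP of 2.0 x ULN and a rise from 1.2 to 2.0 x ULN both appear as high to high.
- The marked-abnormality cut-off for ALP in SAP Table 6-2 is above 5.0 x ULN, so it does not cover 1.5 to 5.0.
- The bilirubin criterion in Table 6-2 is referred to Baseline when Baseline is abnormal, but at 3.0 times the Baseline value. That is a different level from the LFT cut-offs.

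**4. Size under assumptions**

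Let p be the share of the Safety Set above an ALP or bilirubin cut-off at entry and unchanged, and N the Safety Set size. The documents give neither. I take p = 1% and 5% as assumptions. N = 30 is the minimum randomized. N = 75 is the number screened, hence an upper limit.

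- Expected carried-in cases = N x p.
- Chance of at least one = 1 - (1 - p)^N.

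| N | p | Expected | Chance of at least one |
|---|---|---|---|
| 30 | 1% | 0.3 | 1 - 0.99^30 = 0.26 |
| 30 | 5% | 1.5 | 1 - 0.95^30 = 0.785 |
| 75 | 1% | 0.75 | 1 - 0.99^75 = 0.529 |
| 75 | 5% | 3.75 | 1 - 0.95^75 = 0.979 |

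One such participant adds 1/30 = 3.3 percentage points at N = 30, or 1/75 = 1.3 at N = 75.

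**The case against.** Several points on the other side stand.

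- **These are not toxicity cases.** A reader might infer that stable ALP or Gilbert's bilirubin would be reported as liver toxicity or as pDILI. The SAP calls these levels of LFT elevation, and every combined laboratory criterion also needs AST or ALT of at least 3 x ULN. An isolated ALP or bilirubin elevation meets none of them.
- **The post-Baseline row is not a criterion.** Because it sits in a list of criteria, a reader might infer that everyone with a post-dose sample meets one. It is plainly the evaluable-participant row.
- **Baseline values can be traced.** SAP 4.5.3.1.1 lists all laboratory results, Baseline included, with out-of-range values flagged. The protocol also has the cause of a clinically meaningful Baseline elevation recorded. A careful reader could reconstruct each case by hand, although the published count would stay mixed.
- **Entry is narrower than the limits suggest.** Exclusion 1 covers significant laboratory abnormalities in the investigator's opinion, exclusion 16 covers unstable liver or biliary disease, and values above ULN are retested before dosing where possible. This lowers the likely number but does not close the gap.
- **Counting every elevation is a defensible, cautious choice.** Simply dropping participants who met the level at Baseline would create a different blind spot. ALP has a single level, so a rise from 1.6 to 4.9 x ULN would leave the main count, and it would also miss the marked-abnormality table at 5.0. This argues against exclusion; it does not argue against showing Baseline status.

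**Conclusion.** The gap is real but minor. The LFT count has no stated window and no Baseline reference, and the protocol admits participants already above its ALP and bilirubin cut-offs. For those participants an unchanged value is counted without any drug effect. ALT and AST levels are largely protected because their lowest cut-off equals the Screening limit; a rise between Screening and first dose remains possible. The combined criteria are largely unaffected.

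The size is uncertain. The 1% to 5% share is assumed, and the Safety Set size is known only to lie within limits. A reader might infer that carried-in cases would make up most of the reported elevations. The documents give no expected number of elevations, so they do not support that. What can be said is that the ALP and bilirubin percentages cannot be read as new elevations on rozanolixizumab. The table is descriptive, in an estimation study without hypothesis tests, and the primary endpoint is not touched.

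**What to change.** Amend SAP 4.5.3.1.2 as follows.

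1. Restrict the LFT elevation count to post-Baseline values after the first infusion and within 56 days of the last infusion, the window already used in 4.5.3.1.1.
2. Present each ALP and total bilirubin level in two parts: not met at Baseline (treatment-emergent) and already met at Baseline.
3. Add the Baseline value and the maximum post-Baseline value, both as multiples of ULN, to the liver listing, so that a further rise in someone already above the level stays visible.
4. Leave the combined rows of AST or ALT with bilirubin, including potential Hy's Law, without a Baseline filter.

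The cost is SAP wording, one table split and the added listing content. No new data are needed.
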